### Word Recognition Scoring Chart

TABLE 4. Lower and upper limits of the 95% critical differences for percentage scores. Values within the range shown are not significantly different from the value shown in the percentage Score columns ( $p > 0.05$ ).

| % Score | n = 50 | n = 25 | n = 10 | % Score | n = 100* |
|---------|--------|--------|--------|---------|----------|
| 0       | 0-4    | 0-8    | 0-20   | 50      | 37-63    |
| 2       | 0-10   |        |        | 51      | 38-64    |
| 4       | 0-14   | 0-20   |        | 52      | 39-65    |
| 6       | 2-18   |        |        | 53      | 40-66    |
| 8       | 2-22   | 0-28   |        | 54      | 41-67    |
| 10      | 2-24   |        | 0-50   | 55      | 42-68    |
| 12      | 4-26   | 4-32   |        | 56      | 43-69    |
| 14      | 4-30   |        |        | 57      | 44-70    |
| 16      | 6-32   | 4-40   |        | 58      | 45-71    |
| 18      | 6-34   |        |        | 59      | 46-72    |
| 20      | 8-36   | 4-44   | 0-60   | 60      | 47-73    |
| 22      | 8-40   |        |        | 61      | 48-74    |
| 24      | 10-42  | 8-48   |        | 62      | 49-74    |
| 26      | 12-44  |        |        | 63      | 50-75    |
| 28      | 14-46  | 8-52   |        | 64      | 51-76    |
| 30      | 14-48  |        | 10-70  | 65      | 52-77    |
| 32      | 16-50  | 12-56  |        | 66      | 53-78    |
| 34      | 18-52  |        |        | 67      | 54-79    |
| 36      | 20-54  | 16-60  |        | 68      | 55-80    |
| 38      | 22-56  |        |        | 69      | 56-81    |
| 40      | 22-58  | 16-64  | 10-80  | 70      | 57-81    |
| 42      | 24-60  |        |        | 71      | 58-82    |
| 44      | 26-62  | 20-68  |        | 72      | 59-83    |
| 46      | 28-64  |        |        | 73      | 60-84    |
| 48      | 30-66  | 24-72  |        | 74      | 61-85    |
| 50      | 32-68  |        | 10-90  | 75      | 63-86    |
| 52      | 34-70  | 28-76  |        | 76      | 64-86    |
| 54      | 36-72  |        |        | 77      | 65-87    |
| 56      | 38-74  | 32-80  |        | 78      | 66-88    |
| 58      | 40-76  |        |        | 79      | 67-89    |
| 60      | 42-78  | 36-84  | 20-90  | 80      | 68-89    |
| 62      | 44-78  |        |        | 81      | 69-90    |
| 64      | 46-80  | 40-84  |        | 82      | 71-91    |
| 66      | 48-82  |        |        | 83      | 72-92    |
| 68      | 50-84  | 44-88  |        | 84      | 73-92    |
| 70      | 52-86  |        | 30-90  | 85      | 74-93    |
| 72      | 54-86  | 48-92  |        | 86      | 75-94    |
| 74      | 56-88  |        |        | 87      | 77-94    |
| 76      | 58-90  | 52-92  |        | 88      | 78-95    |
| 78      | 60-92  |        |        | 89      | 79-96    |
| 80      | 64-92  | 56-96  | 40-100 | 90      | 81-96    |
| 82      | 66-94  |        |        | 91      | 82-97    |
| 84      | 68-94  | 60-96  |        | 92      | 83-98    |
| 86      | 70-96  |        |        | 93      | 85-98    |
| 88      | 74-96  | 68-96  |        | 94      | 86-99    |
| 90      | 76-98  |        | 50-100 | 95      | 88-99    |
| 92      | 78-98  | 72-100 |        | 96      | 89-99    |
| 94      | 82-98  |        |        | 97      | 91-100   |
| 96      | 86-100 | 80-100 |        | 98      | 92-100   |
| 98      | 90-100 |        |        | 99      | 94-100   |
| 100     | 96-100 | 92-100 | 80-100 | 100     | 97-100   |

\*If score is less than 50%, find % Score = 100-observed score and subtract each critical difference limit from 100.

---

## Version History

SAP Version	Approval Date	Change(s)	Rationale
1.0	26NOV2019	Not Applicable	Original Version
2.0	08OCT2020	Include change from baseline analyses for TFI, HSI, and HHIA. Make updates for Protocol Version 3.0, for interim analysis, and handling of treated/untreated ears for Full Analysis Set and Safety Analysis Set analyses.	Version 2.0
3.0	15JAN2021	Make updates for Protocol Version 4.0 and for interim analysis.	Version 3.0
4.0	10FEB2021	Make updates to unblind at the subject level after the interim analysis, as specified in Protocol Version 5.0. Clarify covariance structure for HSI and HHIA analyses.	Version 4.0

---

## LIST OF ABBREVIATIONS

AC	Air Conduction
AE	Adverse Event
AESI	Adverse Event of Special Interest
AR(1)	Autoregressive (1)
ATC	Anatomical Therapeutic Chemical
BC	Bone Conduction
BCA	Bone Conduction Average
BIC	Bayesian Information Criteria
C-SSRS	Columbia-Suicide Severity Rating Scale
CI	Confidence Interval
CNC	Consonant-Nucleus-Consonant
CRF	Case Report Form
CSR	Clinical Study Report
CTMS	Clinical Trial Management System
dB	Decibel
EHFA	Extended High Frequency Audiometry
FAS	Full Analysis Set
GEE	Generalized Estimating Equation
HHIA	Hearing Handicap Inventory for Adults
HSI	Hearing Screening Inventory
IA	Interim Analysis
ICH	International Conference on Harmonisation
LS	Least Squares
MAR	Missing At Random
MedDRA	Medical Dictionary for Regulatory Activities
MMRM	Mixed-effect Model for Repeated Measures
NIHL	Noise Induced Hearing Loss
NR	No Response
PPAS	Per Protocol Analysis Set
PTA	Pure Tone Average
SAE	Serious Adverse Event
SAP	Statistical Analysis Plan
SD	Standard Deviation
SfAS	Safety Analysis Set
SL	Sensation Level
SPL	Sound Pressure Level
SSNHL	Sudden Sensorineural Hearing Loss

TEAE	Treatment-Emergent Adverse Event
TFI	Tinnitus Functional Index
TM	Tympanic Membrane
TR	Thornton-Raffin
UN	Unstructured
WR	Word Recognition in quiet
WIN	Words-In-Noise testing

## 1. PURPOSE OF THE ANALYSES

The purpose of this statistical analysis plan (SAP) is to provide detailed information to aid in the implementation of the statistical analysis and reporting of the study data for use in the interim analysis (IA) and clinical study report (CSR). It briefly summarizes the protocol, describes the analysis sets that will be analyzed, and describes the analyses to be performed. The details of the specific statistical methods that will be used are provided. If additional analyses are required to supplement the planned analyses described in this SAP, they may be completed and will be identified in the CSR as post hoc. Table, figure, and listing specifications are in separate documents.

Plans for the IA are specified in Section 10.

This SAP was written with due consideration of the recommendations outlined in the most recent International Conference on Harmonisation (ICH) E9 Guideline entitled Guidance for Industry: Statistical Principles for Clinical Trials and the most recent ICH E3 Guideline, entitled Guidance for Industry: Structure and Content of Clinical Study Reports and was finalized prior to unblinding for the interim analysis.

## 2. PROTOCOL SUMMARY

### 2.1. Primary Study Objectives

1. To assess the exploratory efficacy by audiologic response following single and repeat doses of FX-322 in subjects with stable sensorineural hearing loss.
2. To assess the local and systemic safety of single and repeat doses at of FX-322 in subjects with stable sensorineural hearing loss.

### 2.2. Study Design

This is a Phase 2a, prospective, randomized, double-blind, placebo-controlled, single and repeat-dose, multicenter, exploratory efficacy study of FX-322, administered by intratympanic injection, in adults with stable sensorineural hearing loss.

The study will have 3 phases: Screening, Treatment, and Follow-up. The Screening phase can occur up to 30 days prior to study drug administration (Baseline/Treatment Day 1). The Treatment phase will be 21 days (4 treatment visits 7 days apart) and the Follow-up phase will be 7 months from Baseline (Day 1).

#### 2.2.1. Screening

During the Screening phase, all subjects will be screened to determine study eligibility. All subjects will return for the Baseline visit and will be evaluated to ensure they continue to meet appropriate inclusion/exclusion criteria applicable at that visit.

### 2.2.2. Treatment

Approximately 96 subjects are planned to be enrolled in this study. The subjects will be randomized to receive FX-322 or placebo according to the different treatment group schedules listed below:

Group Dosing Schedule					
Treatment Group	# of Subjects	Day 1	Day 8	Day 15	Day 21
1	24	FX-322	Placebo	Placebo	Placebo
2	24	FX-322	FX-322	Placebo	Placebo
3	24	FX-322	FX-322	FX-322	FX-322
4	24	Placebo	Placebo	Placebo	Placebo

Once a subject has been identified as meeting all inclusion/exclusion criteria, the qualifying ear with the worse hearing will be selected, unless a rationale exists to treat the other ear (e.g., the worse hearing ear does not meet the study criteria). The study treatment or placebo will be administered on Day 1, Day 8, Day 15, and Day 21. The placebo will be matched to FX-322 in consistency and color.

Each subject will be placed in the supine position. Topical anesthesia will be administered to the tympanic membrane. Under a microscope, a 25-gauge needle will be used to inject FX-322 or placebo into the middle ear at the junction of the posterior inferior and posterior superior quadrant with the needle tip directed towards the round window. The posterior superior quadrant should be avoided to prevent injury to the ossicles. After injection, the subject will continue to lie with the injected ear facing up for 10-15 minutes. The injections will be performed at an appropriate location designated by a Board-certified Otolaryngologist trained and experienced in performing intratympanic injections. Safety monitoring will include recording of adverse events (AEs), safety laboratory assessments, and monitoring of tympanometry and otoscopic exams.

### 2.2.3. Follow-up

Subjects will be required to return for safety, otologic, and audiologic assessments at Days 15, 60, 90, 150, and 210 after the initial injection. Subjects will be contacted by phone for safety assessments at Days 30, 120, and 180.

### 2.3. Study population

The study population will include male and female adults (18 to 65 years inclusive), otherwise healthy with stable sensorineural hearing loss. Protocol Sections 8.4.2 and 8.4.3 define the inclusion and exclusion criteria for the study.

## 2.4. Sample size

The sample size of approximately 24 subjects per group was considered adequate to explore the potential efficacy of FX-322 associated with various dosing schedules and was not based on formal statistical evaluation.

## 3. GENERAL ANALYSIS AND REPORTING CONVENTIONS

The following is a list of general analysis and reporting conventions to be applied for this study.

- Categorical variables will be summarized using counts (n) and percentages (%) and will be presented in the form n (%). If a count is 0, no percentage will be shown. To ensure completeness, summaries for categorical and discrete variables will include all categories, even if no subjects had a response in a particular category. Missing data for categorical variables will have a 'Missing' category added at the end and the count will be presented without a percentage. Percentages for categorical variables will exclude the 'Missing' category.
- Continuous variables will be summarized using mean, standard deviation (SD), minimum, maximum, median, and number of subjects. The mean, median, and confidence intervals (CI) will be rounded and reported to 1 more level of precision than the original observations, and the SD will be rounded and reported to 2 more levels of precision than the original observations. The minimum and maximum will be the same precision as the original data.
- Following SAS default rules, the median will be reported as the rounded average of the two middle numbers if the dataset contains even numbers.
- P-values will be rounded and reported to 3 decimal places if greater than 0.001. If the rounded p-value is less than 0.001, '<0.001' will be reported. If the rounded p-value is >0.999, '>0.999' will be reported. P-values and significant levels will be reported as 0.05 rather than .05.
- No preliminary rounding will be performed; rounding will only occur after analysis. To round, consider digit to right of last significant digit: if < 5 then round down, if >=5 then round up.
- All listings will be sorted in order of treatment group, subject, and time of assessment (e.g., visit, time, and/or event).
- Dates in listings will be displayed as yyyy-mm-dd (e.g., 2019-08-22).
- Age (in years) will be calculated using the date of birth and the Visit 1 (Screening) date in the following SAS algorithm: `floor((intck('month', date of birth, Visit 1 date)`

- (day(Visit 1 date) < day(date of birth)))/12. In the analysis datasets, tables, and listings, age will be reported as the integer part of the derived age, with no rounding.
- All analysis will be performed using the SAS System version 9.4.
  - All tables that summarize results by treatment group for subjects in the Full Analysis Set (FAS) or Per Protocol Analysis Set (PPAS), defined in Section 4, will include each of the FX-322 treatment groups, a pooled FX-322 treatment group, and the placebo treatment group. Subjects in the FAS or PPAS will be classified into randomized treatment groups based on their randomized treatment.

Randomized Treatment Group	# of Subjects	Day 1	Day 8	Day 15	Day 21
FX-322 1x	24	FX-322	Placebo	Placebo	Placebo
FX-322 2x	24	FX-322	FX-322	Placebo	Placebo
FX-322 4x	24	FX-322	FX-322	FX-322	FX-322
FX-322 Pooled	72	FX-322	Placebo or FX-322	Placebo or FX-322	Placebo or FX-322
Placebo	24	Placebo	Placebo	Placebo	Placebo

- For assessments completed by ear for each subject, the unit of analysis will be the ear and treated and untreated ears will be summarized separately. Treated ears will be defined as the qualified ears for treatment that received at least one dose of study treatment per the randomized treatment schedule, and untreated ears will be the ears not qualified for treatment. For analyses by ear, the treatment group for each ear will be the subject’s randomized treatment group, regardless of actual administration in the given ear. All treated (qualified) ear data will be analyzed, including those with dosing administration errors. All untreated (not qualified) ear data will be analyzed up until any dosing administration error (wrong ear injection). For analyses by ear, data for untreated (not qualified) ears after a dosing administration error will be excluded from FAS and PPAS analyses.
- All tables that summarize results by treatment group for subjects in the Safety Analysis Set (SfAS) will include 1 FX-322 dose received, 2 FX-322 doses received, 4 FX-322 doses received, and placebo (0 FX-322 doses received). For SfAS analyses by subject, all subjects in the SfAS will be classified into actual treatment groups based on the actual number of FX-322 doses received in any ear (qualified or not qualified). In the event that any subject(s) receive 3 FX-322 doses, separate listings for subject(s) receiving 3 FX-322 doses will be created. Subjects receiving 3 FX-322 doses will be included in the total column.

Actual Treatment Group	# of Subjects Planned	Days 1-21
FX-322 1x	24	1 dose of FX-322
FX-322 2x	24	2 doses of FX-322
FX-322 4x	24	4 doses of FX-322
Placebo	24	0 doses of FX-322

For assessments completed by ear for each subject, the unit of analysis will be the ear and treated and untreated ears will be summarized separately. An ear will be considered treated from the time it receives any dose, whether the qualifying ear or not. A subject's treated ear will be classified into an actual treatment group based on the actual number of FX-322 doses received in that ear. An ear will be considered not treated up until the time it receives any dose, whether the qualifying ear or not. Untreated ears will be classified in the Placebo group up until the time it receives any dose, after which the ear will be classified into an actual treatment group based on the actual number of FX-322 doses received in that ear. Pre-dosing measurements will be mapped to treated or untreated based on dosing at Day 1. Subjects with treatment received in the non-qualified ear may contribute more than 1 treated ear to SfAS analyses. In the event that any subject/ear combination(s) receive 3 FX-322 doses, separate reports for subject/ear combination(s) receiving 3 FX-322 doses will be created, as applicable. Subject/ear combination(s) receiving 3 FX-322 doses will be included in the FX-322 total ears column.

For example, a subject treated with FX-322 2x in the qualified ear at Days 1 and 8 and treated with FX-322 2x in the not qualified ear at Days 15 and 21 will be summarized as follows:

- a. For summaries by subject: This subject will be included in the FX-322 4x section of the table.
- b. For summaries by ear:
  - i. The qualified ear data will be reported at all visits in the FX-322 2x section of the table in the Treated column.
  - ii. The not qualified ear data up to and including Day 15 will be reported in the Placebo section of the table in the Untreated column.
  - iii. The not qualified ear data after Day 15 will be reported at visits after Day 15 in the FX-322 2x section of the table in the Treated column.

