### **14.1.7 Safety Analyses**

Safety will be evaluated using the safety analysis set and will include the incidence of adverse events (AEs), serious adverse events (SAE)s, vital signs, clinical laboratory measurements, concomitant medications, otology, questionnaire responses, and tympanometry assessments. Summary descriptive statistics will be provided by actual treatment group, pooled FX-322 group, and overall using the SfAS. No safety data will be imputed except for partial dates if required to determine if an adverse event is treatment emergent or a medication concomitant with exposure to study drug. Details of partial date imputation will be provided in the SAP.

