## 8.3. Adverse Events

All AEs will be recorded from the time of the first treatment through the end of the follow up period. Adverse events occurring for the first time, or worsening in severity, on or after the first dose of study drug or placebo will be considered to be TEAEs. Only TEAEs will be presented in summary tables, but all AEs will be listed with a flag indicating if the AE was treatment-emergent. Adverse events will be coded using the Medical Dictionary for Regulatory Activities (MedDRA) to identify the system organ class and preferred term. The MedDRA version used will be within 1 full version of the latest version at study end. Any ear-related AE, whether occurring in 1 or both ears, will only be counted once in subject incidence counts per system organ class and preferred term.

Treatment-emergent AEs will be summarized by treatment group and overall for all subjects in the SfAS. The summary will display the total number of TEAEs as well as the count and percentage of subjects experiencing any TEAE. The total number of TEAEs and the count and percentage of subjects experiencing at least 1 TEAE in each system organ class and preferred term will also be shown. All percentages will use the number of subjects in the SfAS by treatment group as the denominator. Therefore, if a subject has more than 1 AE within a system organ class, the subject will be counted only once in that system organ class. If a subject has more than 1 AE that codes to the same preferred term, the subject will be counted only once for that preferred term. The tabular summary will be sorted by descending frequency of system organ class and preferred term for overall incidence.

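### SAP 3 leaves out, without declaring it, the pooled FX-322 group that Protocol 14.1.7 requires for safety, and gives three-dose subjects no dose column in the by-subject tables

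*SAP*

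**What the plan says.** Protocol 14.1.7 sets the columns for safety: "Summary descriptive statistics will be provided by actual treatment group, pooled FX-322 group, and overall using the SfAS". Pooled and overall are separate items, so one does not stand in for the other. Safety is the second of the two primary objectives (Protocol 7.1).

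SAP 3 sets two column conventions. For FAS and PPAS, tables "will include each of the FX-322 treatment groups, a pooled FX-322 treatment group, and the placebo treatment group", and the accompanying table has a pooled row with 72 planned subjects. For safety, the rule reads: "subjects in the Safety Analysis Set (SfAS) will include 1 FX-322 dose received, 2 FX-322 doses received, 4 FX-322 doses received, and placebo". The accompanying Actual Treatment Group table has four rows of 24 and no pooled row.

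The by-subject safety sections do not restore the pooled group. SAP 8.3 is typical: "Treatment-emergent AEs will be summarized by treatment group and overall for all subjects in the SfAS". SAP 8.4, 8.4.1, 8.5, 8.6.1, 8.6.2, 8.6.5 and 8.6.6 follow the same pattern.

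For subjects with three FX-322 doses, SAP 3 says that "separate listings for subject(s) receiving 3 FX-322 doses will be created" and that "Subjects receiving 3 FX-322 doses will be included in the total column". The total column is not defined. The parallel rule for ears is more specific: "Subject/ear combination(s) receiving 3 FX-322 doses will be included in the FX-322 total ears column".

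SAP 11, which lists departures from the protocol, names only the dropped multiplicity adjustment.

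**The concern.** The protocol promises a summary that the SAP's own column rule does not produce, and nothing records that the change was intended. The SAP is also uneven within itself: it keeps a pooled group for efficacy and an FX-322 total for ears, but neither for subject-level adverse events, AESIs, laboratory values, vital signs, C-SSRS or concomitant medications.

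The part with most consequence is the three-dose subject. Under Protocol 8.8.3 a missed injection is not made up. Protocol 8.4.4 lists an adverse event among the reasons for discontinuing study drug, and Protocol 13 allows further doses to be reconsidered after AESIs. A subject randomized to 4x who misses one injection, or stops after the third, has three FX-322 doses. The event that led to stopping would then appear in no dose column, and the 4x column would describe those who completed all four FX-322 injections. A pooled column of one or more doses would hold that subject in a clearly labelled FX-322 group.

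**Working it through.** **1. Reproduce the plan's figures.** From SAP 3, 24 subjects are planned per group. Pooled FX-322: 3 × 24 = 72. All subjects: 4 × 24 = 96. Both match the documents.

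**2. Set the column rules side by side.**

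| Source | Dose groups | Placebo | Pooled FX-322 | All subjects |
|---|---|---|---|---|
| Protocol 14.1.7, safety | yes | yes | yes | yes |
| SAP 3, FAS and PPAS | yes | yes | yes | – |
| SAP 3 and 8.3 to 8.6, safety by subject | 1x, 2x, 4x | yes | not named | overall, or an undefined total |
| SAP 3, safety by ear | 1x, 2x, 4x | yes | FX-322 total ears | overall |

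**3. The overall column is not a substitute.** Planned placebo share: 24/96 = 25%. With assumed true event rates of 20% on FX-322 and 5% on placebo, it would show (72 × 0.20 + 24 × 0.05)/96 = (14.4 + 1.2)/96 = 16.25%.

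**4. What can be recovered.** Assume that the overall column holds every subject in the Safety Analysis Set. Each subject belongs to one actual-dose group, so:

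- Counts: overall minus placebo, over overall N minus placebo N. In the example, (15.6 − 1.2)/(96 − 24) = 14.4/72 = 20%.
- Means: (n_o·m_o − n_p·m_p)/(n_o − n_p), with o for overall and p for placebo.
- SDs: each column's sum of squares is (n − 1)s² + n·m². Subtract placebo from overall and solve for s with the pooled n and mean.
- Medians: not recoverable from column summaries.

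SAP 3 reports n, mean and SD for continuous variables, so the first three work, up to rounding.

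**5. Three-dose subjects.** If k of the 24 4x subjects receive three doses and all others are dosed as planned, the three dose columns sum to 72 − k.

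| k | 4x column | Share of 4x lost | Sum of dose columns |
|---|---|---|---|
| 1 | 23 | 4.2% | 71 |
| 2 | 22 | 8.3% | 70 |
| 3 | 21 | 12.5% | 69 |
| 4 | 20 | 16.7% | 68 |

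The documents give no expected k; 1 to 4 is an assumed range. A 4x subject who stops after one or two doses is classed by doses received and does enter the 1x or 2x column, so the gap is specific to three doses.

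**6. Illustration of group size only.** These figures show what one column of 24 or of 72 can say when read alone, assuming one event rate across dose groups. The 2% rate is an assumption. The 4% rate is the upper figure for eardrum perforation that Protocol 6.2 gives from a published trial of intratympanic steroid.

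| Quantity | n = 24 | n = 72 |
|---|---|---|
| One-sided 95% upper bound with zero events, 1 − 0.05^(1/n) | 11.7% | 4.1% |
| Chance of at least one event at 2%, 1 − 0.98^n | 38.4% | 76.7% |
| Chance of at least one event at 4%, 1 − 0.96^n | 62.5% | 94.7% |

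They do not measure information lost by the omission, because every FX-322 subject's events are recorded either way.

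**The case against.** The case for leaving this alone has real force. Safety is descriptive (Protocol 14.1.1), so no planned test or interval is lost. Every event is still tabulated or listed, and by step 4 a reader can obtain pooled counts, means and SDs by subtraction. The risks named in Protocol 6.2 mainly concern the ear and the injection, and by-ear tables already have an FX-322 total. Pooling can also dilute a harm confined to four doses, and the objective concerns single and repeat doses. Finally, the SfAS column list in SAP 3 may not be exhaustive: the same section mentions a total column that the list does not name, and SAP 1 says that table specifications are held separately, so a pooled column may exist there.

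Most of this stands as a limit on the harm, and it rules out three stronger readings that a reader might infer:

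- *That by-subject safety has no comparison of active with placebo.* It does: 1x, 2x and 4x each share a table with placebo. Only the pooled display is missing.
- *That pooled means and SDs for laboratory values and vital signs cannot be rebuilt.* They can, under the assumption in step 4.
- *That three-dose subjects are certainly in no FX-322 column.* This depends on what the total column holds. The phrasing in SAP 8.3 suggests all subjects; the by-ear rule suggests that an FX-322 total could be meant. The text does not settle it.

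The objection does not remove the mismatch. The protocol names the pooled group, the SAP does not provide it for subjects, and SAP 11 is silent. A separate specification that did include it would make the SAP text more in need of correction. The dilution argument is a reason to show the dose groups as well, which both documents already do.

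**Conclusion.** The point holds as an undeclared departure of the SAP from the protocol, with a practical gap for three-dose subjects. It should be corrected, but it does not threaten the trial's safety data.

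Its size is one missing display, 72 planned FX-322 subjects against 24 on placebo, in every by-subject safety table. In addition, 4.2% to 16.7% of the 4x column would have no dose column if one to four such subjects receive three doses. Those subjects are still in the separate listings and in the total column, whatever that proves to contain.

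The conclusion rests on reading the four-group list in SAP 3 as the working rule for by-subject tables, which SAP 8.3 to 8.6 support. That three-dose subjects come only from the 4x arm assumes no dosing errors. The ability to back-calculate assumes that overall means all subjects. If it does, the cost to readers is a subtraction, plus medians that they cannot obtain. They should not have to derive a summary that the protocol promises.

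**What to change.** In SAP 3, add an FX-322 pooled row to the Actual Treatment Group table, defined as one or more FX-322 doses received, including three. Show it as a column in the by-subject safety tables of SAP 8.3 to 8.6, beside placebo and separate from overall. Define the total column in the same section: state whether it holds all subjects or FX-322 subjects only, and use one term for it throughout. Keep the separate listings for three-dose subjects.

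If the sponsor meant to leave the pooled group out of by-subject safety, SAP 11 should say so and give the reason; the total column still needs its definition.

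The cost is one column in tables already planned and a few lines of SAP text. No new data are needed and trial conduct does not change.
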